8.2 Outcome variables

8.2.1 Primary variable

Efficacy in this study will be assessed by difference of AAA diameter determined by CT after 24 and 60 months vs at baseline, expressed as mm/year. The primary outcome is effect on AAA growth rate following 60 months metformin treatment vs standard care.

8.2.2 Secondary variables

Secondary efficacy variables are; 1) difference in log-transformed AAA-volume determined by CT at 24 and 60 months vs at baseline (Log-transformation is undertaken because AAA volumes appear to follow a right-skewed distribution based on in house data), 2) difference in AAA-diameter determined by US at 24 and 60 months vs at baseline, 3) difference in circulating inflammation and matrix remodelling biomarkers assessed by established assays, 4) difference in quality of life score at 24 and 60 months vs at baseline, 5) difference in need for AAA surgery and aneurysm rupture at 24 and 60 months and 6) cost effectiveness of metformin treatment 2 g daily to reduce need for prophylactic surgery of AAA.

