1. BACKGROUND, RATIONALE AND OBJECTIVES

1.1 Background

Abdominal aortic aneurysm (AAA) is a major health issue and ruptured AAA a common cause of death in Europe and North America. In Sweden 700-1000 annual deaths are attributed to AAA. To prevent rupture, early detection and preventive surgical repair in selected individuals is recommended. AAA screening programs are already implemented in the UK, Sweden and the USA. Most screening detected AAAs are, however, small (diameter 30-54 mm) and are under surveillance until expansion to the threshold for elective surgical repair; i.e. diameter ≥55 mm for men and ≥50 mm for women. Presently approximately 15,000 men and women are being monitored for small AAAs in Sweden, of whom 70% eventually will require surgical repair. In 2015, ~1200 AAA repairs were performed in Sweden at a cost of ~30 million Euros (Swedvasc 2016). AAA repair is associated with significant mortality (1-5%), perioperative complications (up to 20%), cost (~25,000 Euros/patient) and need for life-long post-operative follow-up, imaging and repeat surgery (in ~20% of cases) (Mani 2009, Mani 2010, Mani 2013).

A key limitation of contemporary treatment strategies of AAA is the lack of therapy directed at small AAA (Wanhainen 2019). Although surgical repair is an effective treatment for large AAA, several large trials (Powell JT 2007, UKSAT 2002, Lederle 2002, Cao 2011) have shown that early surgery of small AAA does not reduce mortality. Given that AAA diameter is the strongest predictor for rupture and the natural course for AAA is continued expansion, a mean to reduce AAA growth rate would be highly beneficial. Commonly used cardiovascular drugs, such as anti-platelet drugs, statins, angiotensin converting enzyme inhibitors and beta-blockers have not been shown to slow AAA growth in cohort studies (Ferguson 2010, Twine 2011). Previous interventional trials with therapy directed at AAA growth reduction include antibiotics, mast cell inhibitors, beta-blockers, platelet inhibitors, and angiotensin converting enzyme blockers, with trials of stem cells and cyclosporine under way. These trials have all been either small, with negative results or had unacceptable side effects (Meijer 2013, Sillesen 2015, PATI 2002, Golledge 2017, Rughani 2012).

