1.2.2 Secondary objectives

To examine if metformin limits increase in; a) CT-assessed AAA volume; b) ultrasound assessed AAA diameter; c) improves health-related quality of life; d) reduces the need for surgery (diameter ≥55mm) or rupture; and e) represents a cost-effective treatment to reduce the need for AAA surgery.

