2. STUDY PLAN AND PROCEDURES

2.1 Study design

The MAAAGI-trial is a population-based multi-center, prospective, parallel group, randomized, open label trial with blinded outcome assessment to assess if metformin up to 2g daily over a five-year period will reduce AAA growth in patients who do not have diabetes.

Patients will be recruited from a cohort of patients with diagnosed AAA at the following seven Swedish sites; 1) Uppsala University hospital, Uppsala, 2), Skåne University hospital, Malmö, 3) Gävle county hospital, Gävle, 4) Västerås county hospital, Västerås. 5) Karlstad county hospital, Karlstad 6) Falun county hospital, Falun, and 7) Umeå University Hospital, Umeå.

The patients should have a maximum aortic diameter of 30-49mm for men and 30-44mm for women, not have diabetes and be expected to tolerate metformin.

A total of 500 patients with AAA will be included in the study, 250 in each study arm. Patients will be randomised to metformin or standard care in a 1:1 ratio.

The patients are scheduled for one enrolment visit, eight study visits and ten phone contacts for those randomized to metformin (three to support titration of study drug) and seven phone contacts for those randomized to standard care. The study visits will take place at the vascular laboratory at the respective surgical departments for clinical examination and blood sampling and at the CT units at the radiology departments where CT-imaging will be performed.

After a run in phase to support titration of metformin, visits and phone contacts are scheduled to alternate every three months until 24 months and twice yearly thereafter. CT imaging and AAA US will be performed at baseline, 24 months and end of study, as well as if necessary according to clinical routine. Study drug will start at baseline and continue through completion.

End of study is defined as 1) study completion at 60 months, or 2) discontinuation from study before that for any reason, for example due to AAA repair or patients will.

When all patients have completed the 24-month follow-up (including imaging) an interim analysis will be performed to assess for efficacy and safety; if there is no trend towards a positive effect or signs of a harmful effect of metformin, the study will be stopped at this phase.

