5.1.2 Imaging

At baseline, 24 months and completion, the aorta will be examined by non-contrast enhanced CT with 1 mm slices or thinner from the jugulum to the groins.

At enrolment, 24 months and completion the abdominal aorta will be examined by US. The assessment of abdominal aortic diameter with US will be done by the local US technician, using the standardized technique measuring the largest anterior-posterior diameter from leading edge to leading edge perpendicular to the blood flow in the aneurysm. Inclusion criteria will be based on US determined diameter.

If a subject withdraws from the study due to operative need of the aorta, the preoperative CT will be used for analysis in the study. The assessment of aortic diameter on CT will be done using outer edge to outer edge perpendicular to blood flow. Volumetric AAA analysis of CT images will be performed using manual drawing of the vessel wall contours in axial slices of the entire abdominal aortic as well as semiautomatic measures in 3mensio, Pie Medical, Maastricht. Analysis will start at the slice just below the most distal renal artery excluding accessory renal arteries and end at the slice just above the aortic bifurcation. Measures of perivascular adipose tissue will be made adjacent to the aorta.

All CT assessment (diameter and volume) will be done at a core lab at the Department of Radiology, Uppsala university hospital, Uppsala. The CT identification is the four digits enrolment code. The reviewer will be blinded regarding treatment allocation.

CT images will also be reviewed by local radiologists according to GCP at respective hospital. Accidental findings of unrelated pathology on the CT scan will be dealt with as appropriate by investigator at respective site.

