8.3 Statistical analysis

The primary efficacy end-point is the between groups difference in mean annual AAA growth over 60 months. AAA growth will be analysed using an analysis of covariance (ANCOVA) model where AAA growth at 60 months is the dependent variable and treatment group and baseline AAA is included as independent variables. The results will be presented as the estimated group difference with 95 % confidence intervals at 60 months.

Similar methods will be used to assess growth as log transformed CT-volume and ultrasound diameter. Analysis of other outcomes: 1) Laboratory data and perivascular adipose tissue are exploratory endpoints and will be reported with descriptive statistics and evaluated with appropriate inferential statistics, 2) Patient reported outcome (QoL questionnaires) will be analysed using non-parametric test (Wilcoxson rank-sum test), 3) Pre-defined clinical events,

such as AAA-repair, rupture and death, are expected to be few, and the presentations will use descriptive statistics, 4) Economic analysis: Will be performed adopting a health system perspective. The cost-effectiveness analysis will produce an incremental cost effectiveness ratio as an estimated cost per surgical procedure avoided.

Handling of missing values: The primary analyses will be performed among patients with a measured value at the specific time point. However, as the number of missing values might be substantial several sensitivity analyses of the primary analysis will be performed:

- Multiple imputation (with different assumptions)
 - Assume that drop-outs respond according to randomized group
 - Assume that drop-outs respond according to control group
- Fixed imputation depending on reason for drop-out
 - For clinical events, such as AAA-repair, rupture and death, impute worst possible value
 - For other events impute using a maximum likelihood function

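### Need for surgery is tied to a diameter in the objective but analysed as repairs performed, which nothing blinds, and the blinded core-lab CT diameters are not used for this endpoint

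*Combined protocol and SAP*

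**What the plan says.** Section 2.1 describes an "open label trial with blinded outcome assessment". The blinding that is described concerns images. Under 5.1.2 a core lab reads all CT diameters and volumes without knowledge of the arm, and 7.2 says the same of imaging review in general.

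Objective (d) in 1.2.2 asks whether metformin "reduces the need for surgery (diameter ≥55mm) or rupture". The background (1.1) gives the threshold for elective repair as "diameter ≥55 mm for men and ≥50 mm for women".

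In 8.2.2, item 5 is the "difference in need for AAA surgery and aneurysm rupture at 24 and 60 months" and item 6 is the "cost effectiveness of metformin treatment 2 g daily to reduce need for prophylactic surgery of AAA". Section 8.3 places AAA repair with rupture and death among clinical events that should be few and will be described without a test. It reports the economic result as an "incremental cost effectiveness ratio as an estimated cost per surgical procedure avoided".

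On the scan taken before an operation, 5.1.2 says: "If a subject withdraws from the study due to operative need of the aorta, the preoperative CT will be used for analysis in the study". Section 4.2 only permits that use.

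**The concern.** Rupture happens to a patient, whereas elective repair is decided on. In an open-label trial, a view about whether the drug works could lead to an operation sooner in one arm or later in the other. A count of performed repairs cannot separate such decisions from slower growth.

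Objectives (d) and (e) both depend on this count. Because few events are expected, a small number of discretionary decisions could carry weight, above all in a ratio whose denominator is a difference between two small counts. Meanwhile the trial collects blinded diameters that could inform the question and assigns them no part in it.

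**Working it through.** **1. Is there a stated figure to reproduce?** Not for repairs. Section 8.4 sizes growth only: with a difference of 0.30 × 3 = 0.9 mm/year and SD 2.17, n per arm = 2 × (1.960 + 0.842)² × 2.17² / 0.9² = 91.3, so 92 per arm and 184 in total, as stated. Nothing there bears on repairs. The documents give no repair rate and no rate of disagreement between repair decisions and core-lab diameter.

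**2. The endpoint through the sections**

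| Section | Term | Diameter attached? |
|---|---|---|
| 1.1 | elective repair | yes, differs by sex |
| 1.2.2 (d) | need for surgery | yes, one value |
| 8.2.2 item 5 | need for surgery | no |
| 8.2.2 item 6 | need for prophylactic surgery | no |
| 8.3 | AAA repair; procedure avoided | no |

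The objective concerns need, and the analysis section counts procedures. No section names a reader or modality for the threshold, classifies repairs by indication, or compares a repair with the core-lab reading.

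**3. Who knows the arm?** The design is open label, and 6.3 has the drug interrupted around surgery. Additional imaging follows local routine (2.1), and local radiologists also read the CTs (5.1.2). No section says who decides on repair. That the deciding clinicians know the arm is an inference from the design.

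**4. Which use of the blinded CT would help?** Two kinds of decision matter.
- An early repair adds an operation below the threshold. The core-lab reading of the pre-operative CT would show it.
- A deferred repair removes an operation. That patient has no pre-operative CT, so confirming performed repairs changes nothing. The blinded 24- and 60-month CTs can show that the threshold was reached.

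A definition that covers both must therefore use all three scans and must not depend on whether a repair was done.

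**5. The cost ratio.** Let ΔC be the incremental cost and ΔE the procedures avoided through slower growth. Suppose k further procedures are avoided because of decisions alone. Section 1.1 prices a repair at about 25,000 euros, so the observed ratio is roughly (ΔC − 25,000k) / (ΔE + k). Numerator and denominator both move, so the effect cannot be read from the denominator alone. ΔC, ΔE and k are all unknown, so no percentage follows.

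**6. Can the threshold be reached, and does the choice of threshold matter?** Using the mean rate in 8.4 (3 mm/year, or 3 × 0.7 = 2.1 with a 30% reduction) and assuming linear growth:
- Man entering at 49 mm, threshold 55: 6/3 = 2.0 years, or 6/2.1 = 2.9.
- Man entering at 40 mm, threshold 55: 15/3 = 5.0 years, or 15/2.1 = 7.1.
- Woman entering at 44 mm, threshold 50: 6/3 = 2.0 years, or 6/2.1 = 2.9.
- The same woman, threshold 55: 11/3 = 3.7 years, or 11/2.1 = 5.2.

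The event is reachable within 60 months. For some women, the choice between 1.1 and 1.2.2 decides whether it is. These are illustrations: the growth rate comes from MRI, entry is by ultrasound, and 5.1.2 measures CT between outer edges but ultrasound between leading edges.

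**The case against.** The strongest reply is that little depends on this. Repairs are secondary, expected to be few and presented descriptively. The primary endpoint is CT growth read blinded, and no confirmatory claim uses the repair count. That stands, and it sets the priority.

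Second, 1.2.2 already links need to a diameter, and 8.2.2 speaks of need, not of operations done. This stands in part: the endpoint is inconsistently defined, not undefined. But the diameter has no reader or modality, 8.3 counts procedures, and 1.1 differs from 1.2.2.

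Third, both arms receive standard care under the same guidelines (4.1), which limits arm-dependent decisions. That is fair, though it does not exclude them.

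Fourth, a payer bears the cost of every repair, whatever prompted it. Agreed, so performed repairs should stay in the report beside the diameter-based count.

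A reader might go further and infer that the repair result will favour metformin, or that the primary result is compromised. The documents support neither. They do not name the decision-maker, and they give nothing on the direction or size of bias. Repair does reach one sensitivity analysis of the primary endpoint through worst-value imputation (8.3). AAA-related events also enter the harm criterion at the interim analysis (section 10), which does not say whether repairs count.

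**Conclusion.** The point holds as an inconsistency with a cheap remedy. Objective (d) asks about need defined by diameter. The analysis counts operations whose timing nothing blinds, and the blinded diameters are not brought to bear. As planned, a difference in repairs or in cost per procedure avoided could not be attributed to slower growth.

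No size can be given, because the documents hold no repair rate. The conclusion assumes only that those deciding on repair are not blinded, which the open-label design implies and no section contradicts. It would be wrong to infer that checking each performed repair against its CT settles the matter, since deferred repairs would stay invisible. The affected results are secondary and descriptive, and the blinded primary CT endpoint is not directly affected.

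**What to change.** **Reconcile first.** Settle the thresholds in 1.1 and 1.2.2, name the modality to which the threshold applies, and align 4.2, which permits use of the pre-operative CT, with 5.1.2, which requires it.

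**Then amend 8.2.2 item 5 and 8.3.**
- Define need for surgery as rupture, or a blinded core-lab CT diameter that reaches the reconciled threshold on the 24-month, 60-month or pre-operative CT, whether or not a repair was done.
- Beside it, report all performed repairs by arm, split by core-lab diameter at or above versus below the threshold and by documented symptomatic indication. Give core-lab diameter at repair by arm.
- Show below-threshold repairs as a competing event, since they end observation of the threshold event.
- Run the cost-effectiveness ratio on both counts, with costs matched to each.

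Fix these rules before any comparison by arm is seen. The investigators do the analyses (section 8), and the PI may see the data at any time (7.1).

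**Cost.** Plan wording and a small table; no new scans, provided the pre-operative CTs are sent to the core lab. Some acute cases will lack a readable CT and must be classified from records. Patients who leave before a scheduled CT may have no reading (8.4 allows for 30% dropout), so report the number without one by arm.

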8.2.3 Safety variables

Safety variables include differences in drug related AE and GFR.

8.3 Statistical analysis

The primary efficacy end-point is the between groups difference in mean annual AAA growth over 60 months. AAA growth will be analysed using an analysis of covariance (ANCOVA) model where AAA growth at 60 months is the dependent variable and treatment group and baseline AAA is included as independent variables. The results will be presented as the estimated group difference with 95 % confidence intervals at 60 months.

Similar methods will be used to assess growth as log transformed CT-volume and ultrasound diameter. Analysis of other outcomes: 1) Laboratory data and perivascular adipose tissue are exploratory endpoints and will be reported with descriptive statistics and evaluated with appropriate inferential statistics, 2) Patient reported outcome (QoL questionnaires) will be analysed using non-parametric test (Wilcoxson rank-sum test), 3) Pre-defined clinical events,

such as AAA-repair, rupture and death, are expected to be few, and the presentations will use descriptive statistics, 4) Economic analysis: Will be performed adopting a health system perspective. The cost-effectiveness analysis will produce an incremental cost effectiveness ratio as an estimated cost per surgical procedure avoided.

Handling of missing values: The primary analyses will be performed among patients with a measured value at the specific time point. However, as the number of missing values might be substantial several sensitivity analyses of the primary analysis will be performed:

- Multiple imputation (with different assumptions)
 - Assume that drop-outs respond according to randomized group
 - Assume that drop-outs respond according to control group
- Fixed imputation depending on reason for drop-out
 - For clinical events, such as AAA-repair, rupture and death, impute worst possible value
 - For other events impute using a maximum likelihood function

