4.2 Withdrawal from study

Patients may be discontinued from the study at any time, at the discretion of the investigator.

Patients are free to discontinue their participation in the study at any time for any reason.

Patients who discontinue from the study should always be asked about the reason(s) for the discontinuation (and informed about their right not to disclose their reason for doing so) and the presence of any adverse events (AEs). If possible, they should always be seen and assessed by an investigator and asked to perform completion outcome measures, including CT, US and QoL questionnaires. A pre-operative CT may be used for follow up should indication to operate the aorta arise. Adverse events should be followed up.

Study treatment should be stopped in the following cases: development of diabetes, persistent renal failure with GFR<45ml/min, severely deteriorating health, aortic surgery or onset of exclusion criteria.

If the study medication is stopped, patients will be asked to remain in the study and follow the other procedures according to the protocol. All randomised patients remain in the group they were originally allocated to for the purpose of intention-to-treat (ITT) analyses.

Patients who discontinue the study will not be replaced.

Sponsor has to be informed if a patient is withdrawn by any reason before study end. The "End of study" form must be filled out by the investigator and the reason should be stated.

The study number will not be reused if a patient is withdrawn.

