8.1 Analysis set

All patients for whom a signed informed consent was obtained and an eCRF was started will be accounted for.

The Safety Analysis Set will include all patients who received at least one dose of study drug.

An intention-to-treat (ITT) analysis will include all randomised patients who received at least one dose of study drug and for whom at least one post dose observation for an efficacy endpoint is recorded.

The per-protocol analysis (PPA) consists of patients who sufficiently complied with the protocol. Inclusion in the PPA will require at least the following:

- An at least 80% compliance with the intended use will be accepted as per protocol.
- No major protocol deviations.

• Measure of primary efficacy endpoint at 60 months after baseline, and at 24 months for the interim analysis.

All efficacy analyses will be performed as both ITT and PPA. The ITT analyses is to be considered as main and the PPA as supportive.

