8.4 Sample size estimation

Based on in house data and original data from an Australian study of the relationship between metformin and AAA growth (Golledge 2017) it is conservatively estimated that metformin treatment will lead to a 30% reduction in annual AAA growth. This is regarded as a meaningful change which is likely to translate to an important reduction in requirement for AAA repair. MRI data from the Uppsala group show a mean growth rate of 3mm/year, SD 2.17. Thus needing 184 patients for 80% power at a 30% reduced growth rate. CT data will likely show 10-15% larger SD, adding a 30% dropout rate over five years we approximate a need to recruit 500 patients, 250 in each arm, for 80% power at 2-tailed α 0.05.

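### The primary ANCOVA models 60-month growth alone, so the 24-month CT of patients who later leave for non-surgical reasons does not enter the primary estimate

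*Combined protocol and SAP*

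**What the plan says.** Section 5.1.2 sets the imaging schedule: "At baseline, 24 months and completion, the aorta will be examined by non-contrast enhanced CT". Diameters are read at a core lab, blinded to allocation.

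Section 8.3 defines the primary model as an ANCOVA "where AAA growth at 60 months is the dependent variable and treatment group and baseline AAA is included as independent variables". The same section restricts the primary analysis to patients measured at the time point in question. It accepts that many values may be missing and lists sensitivity analyses: multiple imputation (drop-outs behave like their own arm, or like the control arm) and imputation by reason for drop-out (worst value for repair, rupture or death; a maximum-likelihood method for other reasons). No inputs to these imputations are named.

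Three other sections bear on the point.
- Section 8.1 asks, for the ITT set, for patients "for whom at least one post dose observation for an efficacy endpoint is recorded". On that criterion a 24-month CT is enough.
- Section 4.2 says that leavers should, where possible, be "asked to perform completion outcome measures, including CT, US and QoL questionnaires". Section 5.1.2 says the pre-operative CT of surgical leavers will be used. Neither section says how a scan taken before 60 months enters the 60-month model.
- Section 10 analyses the 24-month data by ANCOVA at the interim.

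**The concern.** The ITT set admits patients whom the primary model cannot use. Someone who is scanned at 24 months and then lost without a 60-month value meets the criterion of an efficacy observation but has no outcome in the ANCOVA.

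Two things are at stake. The first is precision, because scans already taken and read are left out. The second is bias. A complete-case ANCOVA is valid only if, given arm and baseline diameter, loss is unrelated to growth. A model that also contains the 24-month CT allows loss to depend on the growth seen by then, which is a weaker assumption. The plan's own allowance of 30% drop-out makes the choice matter.

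That growth might influence who stays is plausible. The trial is open label, and local radiologists also review the CTs, so growth at 24 months can become known. The documents do not state any such link.

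**Working it through.** **Inputs from section 8.4:** "MRI data from the Uppsala group show a mean growth rate of 3mm/year, SD 2.17"; the assumption that "metformin treatment will lead to a 30% reduction in annual AAA growth", so the difference is 0.30 × 3 = 0.90 mm/year; "for 80% power at 2-tailed α 0.05"; CT SD larger by 10% to 15%, that is 2.387 to 2.496; 30% drop-out; 250 recruited per arm, hence 0.70 × 250 = 175 completers and 75 lost per arm.

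**1. The plan's own figure.** n per arm = 2(1.960 + 0.842)² × 2.17² / 0.90² = 91.3, so 92 per arm and 184 in total. This agrees with "Thus needing 184 patients for 80% power at a 30% reduced growth rate".

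**2. Margin in the recruitment target.** With SD 2.387 the same formula gives 111 per arm, 222 in total, and 222/0.70 = 318 recruited. With SD 2.496 it gives 121 per arm, 242 in total, and 242/0.70 = 346 recruited. The target of 500 exceeds both. With 175 completers per arm the standard error (SE) is SD × √(2/175):
- SD 2.387: SE 0.255, power Φ(0.90/0.255 − 1.96) = 94%
- SD 2.496: SE 0.267, power Φ(0.90/0.267 − 1.96) = 92%

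**3. Precision gained by using the 24-month CT.** Let r be the correlation of 24- and 60-month growth, n_c = 175 completers, and n_24 the patients per arm with a 24-month CT only. Neither r nor n_24 is in the documents. I assume r from 0.5 to 0.9 and n_24 from 25 to 75 (one third to all of the 75 losses). When loss is random, the variance of an arm mean is proportional to
- complete case: 1/n_c
- likelihood model: (1 − r²)/n_c + r²/(n_c + n_24)

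| r | n_24 | variance ratio | SE (from 0.267) | effective n per arm |
|---|---|---|---|---|
| 0.5 | 25 | 0.969 | 0.263 | 181 |
| 0.7 | 45 | 0.900 | 0.253 | 194 |
| 0.9 | 75 | 0.757 | 0.232 | 231 |

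The SE falls by about 2%, 5% and 13%.

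**4. Bias if loss depends on observed growth.** This was a simulation with very large arms and annualised growth of SD 2.496 at both visits. Loss after month 24 was logistic in observed 24-month growth, with an odds ratio of 1.5 to 3 per SD. Half or all of the loss came late, and r was again 0.5 to 0.9. Baseline diameter was left out, so the SD stands for the SD given baseline. The likelihood estimate regresses 60-month on 24-month growth among completers within arm and averages over everyone with a 24-month CT.

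| Loss mechanism | True effect | Complete case | Likelihood |
|---|---|---|---|
| Same in both arms | 0.90 | 0.79 to 0.89 | 0.89 to 0.92 |
| Same in both arms | 0 | about 0 | about 0 |
| Growth-related in control arm only | 0.90 | 0.29 to 0.81 | 0.89 to 0.92 |
| Growth-related in control arm only | 0 | −0.09 to −0.61 | about 0 |

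With a common mechanism the attenuation is 0.01 to 0.11 mm/year, or 1% to 12% of 0.90. At 0.79 the power is still Φ(0.79/0.267 − 1.96) = 84%.

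**The case against.** The plan already has a remedy. It foresees substantial missingness and prespecifies several sensitivity analyses, including likelihood-based imputation for the very patients at issue. A baseline-adjusted ANCOVA backed by such analyses is an accepted choice. This stands in part. Those analyses could use the 24-month CT, but the plan does not say that they do, and the headline result remains complete-case.

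A reader might infer that the 24-month CT is never used. The documents do not support that: section 10 analyses it at the interim. The interim estimate does not, however, repair the 60-month one.

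A reader might also infer that every late leaver contributes nothing. That is not established. Section 2.1 counts early discontinuation as end of study and schedules a CT there, and growth is expressed per year, so an exit scan could be annualised. The restriction in section 8.3 to the specific time point suggests the opposite. The rule is undefined.

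Nor do the documents show that loss is tied to growth. The most direct route from fast growth to loss is repair, and for those patients the pre-operative CT is to be used. The 30% is not split by reason either, so 75 late non-surgical losses per arm is an extreme. Both points stand. The bias figures are conditional on an assumed mechanism, and the upper end of the precision gain is unlikely.

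**Conclusion.** The point holds in a limited form. The primary analysis omits the 24-month CT of non-surgical leavers who have no 60-month value, and a better method is available from scans already scheduled.

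The precision cost is small, about 2% to 13% of the SE under the assumed ranges. A reader might take it to mean an underpowered trial. It does not, since the recruitment target gives 92% to 94% power on the plan's own inputs.

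Bias is the weightier part, but it is conditional. It requires non-surgical loss to depend on observed 24-month growth, together with either a true treatment effect or a mechanism that differs by arm. With a common mechanism a true 0.90 mm/year becomes about 0.79 to 0.89, which is modest and toward the null, and no false effect is created when there is none. Only an arm-specific mechanism produces large errors, and nothing in the documents says that one is expected.

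This change should be made, but the trial's validity does not turn on it.

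**What to change.** Make the primary analysis a repeated-measures likelihood model of CT diameter change at 24 and 60 months, with treatment-by-visit and baseline-by-visit terms and an unstructured covariance. Report the 60-month contrast divided by 5, in mm/year. With complete data this gives essentially the ANCOVA result. Keep the stated ANCOVA and the imputation analyses as supportive.

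If the ANCOVA stays primary, the minimum is to name the 24-month CT as an input to the imputation models.

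In either case, state how CTs taken before 60 months, both pre-operative and exit scans, enter the analysis. The fixed-visit model does not place them by itself. One option is a sensitivity model with random slopes that enters each scan at its actual date. Apply the same approach to log volume and ultrasound diameter.

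The cost is revised analysis wording and a little programming, with no new visits or scans. The model relies on data being missing at random given baseline and the 24-month CT, which is weaker than the present assumption but still an assumption. Because the trial is open label and the investigators run the analyses, settle the change before outcome data are examined, and so before the 24-month interim.
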